9.4 Statistical Analyses

The statistical analysis plan will be developed and finalized before database lock. Below is a summary of the timing and methods for the planned statistical analyses. To preserve study integrity, the final analysis will be conducted and reported following the end of study, as defined in Section 4.4.1.

9.4.1 Planned Analyses

9.4.1.1 Interim Analysis and Early Stopping Guidelines

9.4.1.1.1 Cohort 1 (Dose Exploration – first 6 DLT-evaluable subjects in cohort)

Safety data will be reviewed on an ongoing basis. The first DLRM will occur after the first 6 DLT-evaluable subjects enrolled in cohort 1 have the opportunity to receive 21 days treatment. In the dose level review meetings, Amgen, in consultation with the site investigators, will review all available cumulative data by cohort prior to making dose determination recommendations. Adverse events and DLTs observed in all subjects will be evaluated continually and fully integrated into all dose level review meetings and considered in all enrollment and dosing recommendations. Additional details regarding the dose review meeting are providing in Section 11.3.

The DLRT will be composed of the investigators, Amgen Medical Monitor, Amgen Global Safety Officer (GSO), Amgen Early Clinical Development Manager, and Biostatistics representative. Additional members may be added as needed (eg, PK Scientist). A quorum, defined as the majority of actively screening and enrolling investigators or their qualified designee (ie, sub-investigator possessing hard copy documentation [eg, email] of the investigator's recommendation regarding the dose level review), must be in attendance for DLRM to proceed. The DLRM will be rescheduled if a quorum is not reached. Voting members of the DLRM will include the Amgen Medical Monitor, the Amgen GSO, and all actively screening and enrolling investigators or their qualified sub-investigator designee.

The team may recommend de-escalation to a lower dose, or termination of the study. The Amgen Medical Monitor and GSO and the majority of actively screening and enrolling investigators participating in the DLRM must cast a positive vote indicating an acceptable safety profile was observed for AMG 510 to allow the dose level modification and/or cohort continuation/expansion to proceed. Available study data including demographics, smoking status (prior and current), medical history, concomitant medications, **adverse events**, ECGs, vital signs, laboratory results, emerging PK or pharmacodynamics, and emerging efficacy data will be reviewed.

The following recommendations will be made by the DLRT:

- dose de-escalation recommendations
- number of subjects per cohort
- continuation, delay or termination of dosing
- change of the dosing schedule
- termination of the study

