For a DLRM to occur, the Medical Monitor must attend, and the GSO or delegate must attend. In addition, a quorum of site investigators must be present. A quorum is defined as the majority of actively screening and enrolling investigators or their qualified designees (ie, sub-investigator possessing hard copy documentation [eg, email] of the investigator's recommendation regarding the dose level review). The DLRM will be rescheduled if these requirements are not met.

Available study data, including demographics, smoking status (prior and current), medical history, concomitant medications, adverse events, electrocardiograms (ECGs), vital signs, laboratory results, emerging PK or pharmacodynamics, and emerging efficacy data will be reviewed.

Dose Level Review Meeting voting will occur as follows: there will be a total of 3 votes, 1 for the Medical Monitor, 1 for the GSO or delegate, and 1 for all of the site investigators or delegates combined. Regardless of how many site investigators there are, all of the site investigators combined will have a total of 1 vote decided by a majority of the investigators (defined as greater than or equal to 50%).

DLRM recommendations to escalate to the next planned cohort (if applicable), must be by unanimous vote. If the voting members of the DLRT are not able to reach a

unanimous recommendation on whether to escalate to the next planned cohort or to an intermediate cohort, then this should be reflected in the DLRM Memo (FORM-115760). Other recommendations, such as expanding a cohort or lowering a dose will be made by a majority vote.

Regulatory and Ethical Considerations

This study will be conducted in accordance with the protocol and with:

- Consensus ethical principles derived from international guidelines including the Declaration of Helsinki and Council for International Organizations of Medical Sciences International Ethical Guidelines
- Applicable International Conference on Harmonisation (ICH) Good Clinical Practice (GCP) Guidelines
- Applicable ICH laws and regulations

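### Cohort expansion has two voting rules: protocol 9.4.1.1.1 and SAP 7.1.1 need all three parties to vote yes, while protocol Appendix 3 needs only two votes of three

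*Protocol*

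**What the plan says.** Protocol 9.4.1.1.1 sets the condition for the first dose level review meeting (DLRM). It names three parties: "The Amgen Medical Monitor and GSO and the majority of actively screening and enrolling investigators participating in the DLRM". What it asks of all three is that they "must cast a positive vote indicating an acceptable safety profile was observed for AMG 510 to allow the dose level modification and/or cohort continuation/expansion". SAP 7.1.1 repeats it in the same words. Just before this, the protocol says: "The team may recommend de-escalation to a lower dose, or termination of the study".

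Protocol Appendix 3 (Section 11.3) describes the vote at the same meeting. It opens with "Dose Level Review Meeting voting will occur as follows" and continues:

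- "there will be a total of 3 votes, 1 for the Medical Monitor, 1 for the GSO or delegate", with the third vote going to the investigators;
- "all of the site investigators combined will have a total of 1 vote decided by a majority of the investigators", where a majority is defined as at least 50%;
- unanimity is required for escalating to a next planned cohort;
- "Other recommendations, such as expanding a cohort or lowering a dose will be made by a majority vote".

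The link between the two texts is a pointer in 9.4.1.1.1: "Additional details regarding the dose review meeting are providing in Section 11.3". SAP 7.1.1 and protocol 6.2.1 have similar pointers. All of them promise more information, and none assigns precedence.

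Protocol 9.2 and SAP 3.2 make the additional subjects at 960 mg (up to 6) depend on the dose level review team (DLRT) recommending that dose as safe and tolerable. Protocol 9.4.1.1.2 and SAP 7.1.2 apply the same procedure to cohort 2.

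**The concern.** Both texts name cohort expansion, and they set different thresholds for it. After a split vote in favour, a reader of Appendix 3 would record a recommendation to expand. A reader of 9.4.1.1.1 or the SAP would record that expansion may not proceed. That recommendation is the gate to enrolling up to 6 more subjects, so the two texts must give the same answer.

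The conflict also determines who holds a veto. The Medical Monitor and the GSO are both sponsor roles. If both vote yes and the investigators vote no, Appendix 3 yields a recommendation to expand, whereas under 9.4.1.1.1 and the SAP the investigators' vote stops it.

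Two related points are unclear. The first is whose votes form the investigators' result and how a tie counts. The second is whether the condition in 9.4.1.1.1 also governs lowering the dose. The term used there for changing the dose level appears to include a reduction, but a vote that safety was acceptable fits poorly with a reduction prompted by toxicity.

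**Working it through.** The plan gives no figure for this point, so there is none to reproduce. The check applies both rules to every possible vote.

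**Step 1: the three votes.** Let M, G and I be 1 for yes and 0 for no, for the Medical Monitor, the GSO and the investigators' combined result. Assume for now that I is the same under both texts.

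- Rule A (protocol 9.4.1.1.1, SAP 7.1.1): proceed if M = G = I = 1.
- Rule B (protocol Appendix 3, for expansion): recommend if M + G + I ≥ 2.

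| M | G | I | Rule A | Rule B | Agree? |
|---|---|---|---|---|---|
| 0 | 0 | 0 | no | no | yes |
| 0 | 0 | 1 | no | no | yes |
| 0 | 1 | 0 | no | no | yes |
| 1 | 0 | 0 | no | no | yes |
| 0 | 1 | 1 | no | yes | **no** |
| 1 | 0 | 1 | no | yes | **no** |
| 1 | 1 | 0 | no | yes | **no** |
| 1 | 1 | 1 | yes | yes | yes |

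Rule A passes 1 of 8 patterns and rule B passes 4 of 8. Every pass under A is also a pass under B, so they disagree in 4 − 1 = 3 of 8. These are counts of patterns, not probabilities.

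**Step 2: ties among investigators.** Appendix 3 counts exactly 50% as a majority. Protocol 9.4.1.1.1 and the SAP leave the term undefined. Protocol 4.2.2 expects about 2 to 4 sites. Assume one voter per site, the same n voters under both texts and no abstentions. Let k be the number of investigator ballots that give I = 1. Appendix 3 passes 2^n + 2k of the 2^(n+2) individual ballots, using its own k at ≥ 50%. The first term has M and G both yes, and the second has exactly one of them yes. Rule A passes k.

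| n | All ballots | Appendix 3 passes | Rule A, majority ≥ 50% | Rule A, majority > 50% | Disagreement |
|---|---|---|---|---|---|
| 2 | 16 | 4 + 2×3 = 10 | 3 | 1 | 7 or 9 |
| 3 | 32 | 8 + 2×4 = 16 | 4 | 4 | 12 |
| 4 | 64 | 16 + 2×11 = 38 | 11 | 5 | 27 or 33 |

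Where a row gives two values, the difference is the tied ballots with M and G both yes: 2 for n = 2 and 6 for n = 4. With n = 3 no tie is possible. On the > 50% reading such a tie is a 3-0 recommendation under Appendix 3 and a bar under rule A.

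**Step 3: whose votes count.** Rule A counts investigators who are currently screening and enrolling and who take part in the meeting. Appendix 3 gives the vote to all site investigators or their delegates. As an illustration, assume 4 site investigators, of whom 2 are active and take part. If those 2 vote no and the other 2 vote yes, Appendix 3 sees 2/4 = 50%, a yes, while rule A sees 0/2.

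**Step 4: can the texts be read together?** Appendix 3 gives the purpose of the meeting as recommending on de-escalation, continuation and expansion, so it is not text about some other decision. Applying the stricter rule throughout would leave its majority sentence with no effect on expansion.

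**The case against.** The best counter-reading is that the rules work in layers: Appendix 3 governs how a recommendation is formed, and 9.4.1.1.1 adds a condition before expansion may proceed. One meeting could then produce a recommendation that is not acted on, without contradiction. The documents do not state this reading, and it fits them poorly. Protocol 9.4.1.1.1 describes a vote by the members of the same meeting and lists the outputs as DLRT recommendations. The sponsor's final decision in protocol 6.2.1 is a separate, later step.

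The practical consequence is limited, and that part of the objection stands. The DLT counts already frame the choice, the sponsor decides after the vote, and the Medical Monitor can suspend dosing at any time. These safeguards help most when a sponsor voter dissents. They help least when the investigators do, because the final decision then rests with the side already in favour.

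Some secondary points deserve less weight:

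- The tie conflict disappears if the 50% definition in Appendix 3 is carried over to 9.4.1.1.1.
- The example of differing electorates is hypothetical. Appendix 3 bases its quorum on the same active investigators, and sites that do not enrol may be closed.
- The dose-lowering conflict is an ambiguity, not a firm contradiction.
- An unscheduled DLRM is affected only if continuation, expansion or a dose change is put to the vote.

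None of these touches the conflict over expansion.

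**Conclusion.** The concern holds. For cohort expansion the protocol contradicts itself, and the SAP repeats one side. Given the same investigator result under both texts, the outcomes are opposite in 3 of 8 vote patterns. A tied investigator vote adds a further conflict only if the undefined majority means more than 50%, and only with an even number of voters.

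Both planned reviews are exposed. Each expansion decision concerns up to 6 subjects, that is, a cohort of 6 or one of up to 12. Unanimous votes are unaffected if the investigator result is the same under both texts. No planned sample size, analysis set or estimate depends on the answer. This should be fixed because it is a conflicting decision threshold in the dose review, even though it changes no statistical result.

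**What to change.** Reconcile the passages so that one voting rule appears in identical terms in protocol 9.4.1.1.1, protocol Appendix 3 and SAP 7.1.1. The rule should state:

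1. which vote is needed to continue or expand a cohort;
2. which vote is needed to lower the dose or stop;
3. which investigators are counted;
4. how a tie among them is treated.

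The sponsor chooses the rule; this review does not favour either version. The cost is wording in two protocol sections and one SAP section. The documents do not say whether a DLRM has already been held. If one has, it would help to record which rule was applied.

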9.4.1.1.2 Cohort 2 (Dose Exploration – first 6 DLT-evaluable subjects in cohort)

If in cohort 1, DLRT makes the recommendation to open cohort 2 (720 mg), the second dose level review meeting will occur after the sixth subject enrolled in cohort 2 has had the opportunity to receive 21 days of treatment.

The same DLRT will be responsible for reviewing all cumulative available data by cohort. The same procedure and principal described in cohort 1 dose level review meeting will be applied in cohort 2 as well.

9.4.1.2 Primary Analysis

The primary analysis will occur after all subjects (6 to 12 subjects) enrolled in cohort 1 and after all 6 to 12 subjects enrolled in cohort 2 (if \ge 2 DLTs are observed in the first 6 subjects in cohort 1) have had the opportunity to complete 6 months on study or have been withdrawn from study.

9.4.1.3 Final Analysis

A final analysis is planned after all cohorts have ended the study. Primary and final analysis may be combined in case all subjects have ended study close to the time point of the primary analysis.

9.4.2 Methods of Analyses

9.4.2.1 General Considerations

Descriptive statistics will be provided for selected demographics, safety, PK, and preliminary efficacy data by dose, and time as appropriate. Descriptive statistics on continuous data will include means, medians, standard deviations and ranges, while categorical data will be summarized using frequency counts and percentages. Subject listings for time-to-event endpoints may be provided instead of Kaplan-Meier estimates or Clopper Pearson exact confidence interval if the analysis set has fewer than 10 subjects. Graphical summaries of the data may also be presented.

Endpoint	Statistical Analysis Methods	
Primary	Not applicable to the study	
Secondary Listings of secondary efficacy endpoints will be produced for all subject The proportion of subjects with an objective response, defined as CR (assessed per RECIST version 1.1) will be described. Similarly for proportion of subjects with disease control, defined as CR + PR + SD be described.		
	For all subjects treated at the planned dose, the Kaplan-Meier method will be used for time-to-event endpoints to estimate the survival curve, quartiles, and rates at selected timepoints with 95% CI for 1) duration of response, 2) progression-free survival, and 3) duration of stable disease. Event-free rates at 3-month intervals will be estimated using the Kaplan-Meier method for progression-free survival (PFS).	
	Time to response will be summarized by the nonmissing sample size (n), standard deviation, median, minimum, and maximum for responders. For secondary endpoint definitions, refer to the statistical analysis plan.	

9.4.2.2 Efficacy Analyses

9.4.2.3 Safety Analyses

9.4.2.3.1 Analyses of Primary Safety Endpoint(s)

Endpoint	Statistical Analysis Methods
Primary	Unless otherwise specified, statistical analyses on safety endpoints will be done using subjects from the safety analysis set, which includes subjects that are enrolled and received AMG 510. The statistical analysis methods are described in Section 9.4.2.3.2 through Section 9.4.2.3.5.

9.4.2.3.2 Adverse Events

Subject incidence of all treatment-emergent adverse events will be tabulated by system organ class and preferred term. Tables of fatal adverse events, serious adverse events, adverse events leading to withdrawal from investigational product, and adverse events of interest (if applicable) will also be provided.

9.4.2.3.3 Laboratory Test Results

Summaries of laboratory data over time and/or changes from baseline over time will be provided. Tables of maximum shifts from baseline to the worst on-study value will be provided for selected laboratory values with National Cancer Institute-CTCAE grades.

9.4.2.3.4 Vital Signs

Summaries of vital signs data over time and/or changes from baseline over time will be provided.

9.4.2.3.5 Electrocardiogram

Summaries over time and/or changes from baseline over time will be provided for all ECG parameters. Subjects' maximum change from baseline in QTcF will be categorized and the number and percentage of subjects in each group will be summarized. Subjects' maximum post baseline values will also be categorized and the number and percentage of subjects in each group will be summarized.

All on-study ECG data will be listed.

9.4.2.3.6 Exposure to Investigational Product

Descriptive statistics of cumulative dose, number of cycles, duration of usage, number and percentage of subjects with dose modifications and reasons will be produced to describe the exposure to AMG 510.

Subject-level data may be provided instead of the summary if the subject incidence is low or single dose is given.

9.4.2.3.7 Exposure to Concomitant Medication

Number and proportion of subjects receiving concomitant medication will be summarized by preferred term as coded by the World Health Organization Drug Dictionary.

World Health Organization. 2018 Statistics. Accessed at: https://www.who.int/news room/fact-sheets/detail/cancer on 12 July 2019.

11. Appendices

Abbreviation or Term	Definition/Explanation
ALP	alkaline phosphatase
ALT	alanine aminotransferase
Anti-HBs	hepatitis B surface antibody
AST	aspartate aminotransferase
AUC	area under the plasma concentration time curve
BCRP	breast cancer resistance protein
CFR	U.S. Code of Federal Regulations
C _{max}	maximum observed plasma concentration
COVID-19	coronavirus disease 2019
CR	complete response
CRC	colorectal cancer
CRF	Case Report Form
СТ	computed tomography
CTCAE	Common Terminology Criteria for Adverse Events
СҮР	cytochrome P450
DDI	drug-drug interactions
DES	Amgen data element standard
DILI	drug induced liver injury
DLRM	dose level review meeting
DLRT	dose level review team
DLT	dose-limiting toxicity
ECG	electrocardiogram
ECOG	Eastern Cooperative Oncology Group
eCRF	electronic case report form
EDC	electronic data capture
EGFR	epidermal growth factor receptor
Electronic Source Data (eSource)	source data captured initially into a permanent electronic record used for the reconstruction and evaluation of a trial.
EMR	Electronic Medical Record
End of Follow-up	defined as when the last subject completes the last protocol-specified assessment in the study
End of Study for Individual Subject	defined as the last day that protocol-specified procedures are conducted for an individual subject
End of Study (primary completion)	defined as the date when the last subject is assessed or receives an intervention for the final collection of data for the primary endpoint(s), for the purposes of conducting the primary analysis, whether the study concluded as planned in the protocol or was terminated early

11.1 Appendix 1. List of Abbreviations and Definitions of Terms

Abbreviation or Term	Definition/Explanation		
End of Study (end of trial)	defined as the date when the last subject across all sites is assessed or receives an intervention for evaluation in the stud (ie, last subject last visit), following any additional parts in the study, as applicable		
End of Treatment	defined as the last assessment for the protocol-specified treatment phase of the study for an individual subject		
ERK	extracellular signal-regulated kinase		
FDA	Food and Drug Administration		
FFPE	formalin-fixed paraffin-embedded		
FIH	first-in-human		
FSH	follicle stimulating hormone		
GCP	Good Clinical Practice		
GDP	guanosine diphosphate		
GI	gastrointestinal		
GLP	Good Laboratory Practice		
GSO	Global Safety Officer		
GTP	guanosine triphosphate		
Нер	hepatitis		
HepBsAg	hepatitis B surface antigen		
HbA1c	hemoglobin A1c		
HIV	human immunodeficiency virus		
HNSTD	highest nonseverely toxic dose		
HRT	hormonal replacement therapy		
IC ₅₀	half-maximal inhibitory concentration		
ICF	informed consent form		
ICH	International Conference on Harmonisation		
IEC	Independent Ethics Committee		
ILD	interstitial lung disease		
INR	international normalized ratio		
IPIM	Investigational Product Instruction Manual		
IRB	Institutional Review Board		
IV	intravenous		
KRAS	Kirsten rat sarcoma		
MATE1	multidrug and toxin extrusion protein 1		
MCV	mean corpuscular volume		
MDRD	Modification of Diet in Renal Disease		
MRI	magnetic resonance imaging		
MSI-H	microsatellite instability-high		

Abbreviation or Term	Definition/Explanation	
NCT	National Clinical Trials	
NE	not evaluable	
NSCLC	non-small cell lung cancer	
PD	progressive disease	
PD-1	programmed cell death protein 1	
PD-L1	programmed death-ligand 1	
PFS	progression-free survival	
P-gp	P-glycoprotein	
РК	pharmacokinetics	
PO	administered orally	
PPI	proton pump inhibitor	
PR	partial response	
Q2C	every other cycle from cycle 7 and beyond	
QC	every cycle from cycle 7 and beyond	
QD	once daily	
QTc	corrected QT interval	
RAF	rapidly accelerated fibrosarcoma	
RBC	red blood cell	
RECIST	Response Evaluation Criteria in Solid Tumors	
rSDR/V	remote Source Data Review and Verification	
Screen	screening	
SD	stable disease	
SFU	safety follow-up	
SGOT	serum glutamic-oxaloacetic transaminase	
SGPT	serum glutamic-pyruvic transaminase	
SOS1	son-of-sevenless homolog 1	
Source Data	information from an original record or certified copy of the original record containing patient information for use in clinical research. The information may include, but is not limited to, clinical findings, observations, or other activities in a clinical trial necessary for the reconstruction and evaluation of the trial. Source data are contained in source documents (original records or certified copies). (ICH Guideline [E6]). Examples of source data include Subject identification, Randomization identification, and Stratification Value.	
STD ₁₀	severely toxic dose in 10%	
Study day 1	defined as the first day that protocol-specified investigational product(s)/protocol-required therapies is/are administered to the subject	
TBL	total bilirubin	

Abbreviation or Term	Definition/Explanation
t _{1/2,z}	terminal half-life associated with λ_z
t _{max}	time to achieve C _{max}
ULN	upper limit of normal
VEGF	vascular endothelial growth factor
WBC	white blood cell

11.2 Appendix 2. Clinical Laboratory Tests

The tests detailed in Table 11-1 will be performed by the central laboratory and/or by the local laboratory.

Protocol-specific requirements for inclusion or exclusion of subjects are detailed in Sections 5.1 to 5.2 of the protocol.

Additional tests may be performed at any time during the study as determined necessary by the investigator or required by local regulations.

Local Laboratory: Chemistry	Local Laboratory: Coagulation	Local Laboratory: Urinalysis	Local Laboratory: Hematology	Central Laboratory
sodium potassium chloride bicarbonate total protein albumin calcium magnesium phosphorus glucose BUN or urea creatinine total creatine kinase total bilirubin direct bilirubin direct bilirubin ALP AST (SGOT) ALT (SGPT) Glomerular filtration rate (derived)	PT/INR PTT/aPTT fibrinogen (optional) D-dimer (optional) Local Laboratory: Serology Hep B surface antigen Hep C antibody Anti-HBs Local Laboratory: Thyroid Panel TSH Total T3 (or free T3 per local standard) Free T4 Local Laboratory: Lipid Panel total cholesterol LDL	specific gravity pH blood protein glucose bilirubin ketones sodium (optional) potassium (optional) Microscopic exam ^c : • cellular casts • granular casts • hemoglobin casts • hyaline casts • hyaline casts • mixed casts • WBC • RBC • epithelial cells • bacteria • urine casts	RBC hemoglobin hematocrit MCV platelets calculated absolute neutrophil count (derived) WBC differential: • total neutrophils • bosophils • basophils • lymphocytes • monocytes	PK sampling tumor biopsy ^b

Table 11-1. Analyte Listing

Local Laboratory: Chemistry	Local Laboratory: Coagulation	Local Laboratory: Urinalysis	Local Laboratory: Hematology	Central Laboratory
	HDL			
	triglycerides			
	Local Laboratory: Other			
	HbA1c			
	Serum or urine pregnancy ^a			

Footnotes defined on next page

ALP = alkaline phosphatase; ALT = alanine aminotransferase; aPTT = activated partial thromboplastin time; AST = aspartate aminotransferase; BUN = blood urea nitrogen; HbA1c = hemoglobin A1c; HDL = high density lipoprotein; Hep = hepatitis; HIV = human immunodeficiency virus; INR = international normalized ratio; LDL = low density lipoprotein; MCV = mean corpuscular volume; PK = pharmacokinetics; PT = prothrombin time; PTT = partial thromboplastin time; RBC = red blood cell count; SGOT = serum

glutamic-oxaloacetic transaminase; SGPT = serum glutamic-pyruvic transaminase; T3 = triiodothyronine; T4 = thyroxine; TSH = thyroid-stimulating hormone; WBC = white blood cell count.

Note: For creatinine clearance calculation, Modification of Diet in Renal Disease formula should be used: GFR (mL/min/1.73 m²) = 175 x SCr (mg/dL)^{-1.154} x age^{-0.203} x 0.742 (if female) x 1.21 (if African American) x 0.763 (if Japanese) x 1.233 (if Chinese).

^a For female subjects of childbearing potential only. At screening, a highly sensitive serum pregnancy test is required. For all other time points, a highly sensitive serum or urine pregnancy test is required.

^b Only applicable if *KRAS p.G12C* status is unknown at screening. Archived FFPE tumor tissue is acceptable. If archived tumor tissue is not available, a tumor biopsy may be performed. Testing for *KRAS p.G12C* can be performed locally or centrally.

^c Microscopic exam to be performed at the discretion of the investigator.

11.3Appendix 3. Study Governance ConsiderationsDose Level Review Meetings (DLRM)

A DLRM is conducted to review and interpret safety data for the purposes of making recommendations dose level de-escalation, cohort continuation, or cohort expansion; making recommendations about non-dose escalation cohorts (eg, expanded, highest dose and/or final cohort); and evaluating safety signals for purposes of applying Dose Cohort Stopping Rules. The required Dose Level Review Team (DLRT) members are the Medical Monitor, Global Safety Officer (GSO), and site investigators. The DLRT will include all site investigators. The Medical Monitor, GSO, and site investigators are the only voting DLRT members. Additional members may be added as needed (eg, Pharmacokinetics [PK] Scientist).

The Medical Monitor must be in attendance and cannot be represented by a voting designee or delegate. Voting designees can be identified as appropriate by the GSO or site investigator(s). A site investigator may identify a delegate (eg, sub-investigator) who is listed in the Delegation of Authority. If a site investigator does this, the site investigator must provide written agreement with the designee or delegate's vote.

For a DLRM to occur, the Medical Monitor must attend, and the GSO or delegate must attend. In addition, a quorum of site investigators must be present. A quorum is defined as the majority of actively screening and enrolling investigators or their qualified designees (ie, sub-investigator possessing hard copy documentation [eg, email] of the investigator's recommendation regarding the dose level review). The DLRM will be rescheduled if these requirements are not met.

Available study data, including demographics, smoking status (prior and current), medical history, concomitant medications, adverse events, electrocardiograms (ECGs), vital signs, laboratory results, emerging PK or pharmacodynamics, and emerging efficacy data will be reviewed.

Dose Level Review Meeting voting will occur as follows: there will be a total of 3 votes, 1 for the Medical Monitor, 1 for the GSO or delegate, and 1 for all of the site investigators or delegates combined. Regardless of how many site investigators there are, all of the site investigators combined will have a total of 1 vote decided by a majority of the investigators (defined as greater than or equal to 50%).

DLRM recommendations to escalate to the next planned cohort (if applicable), must be by unanimous vote. If the voting members of the DLRT are not able to reach a

unanimous recommendation on whether to escalate to the next planned cohort or to an intermediate cohort, then this should be reflected in the DLRM Memo (FORM-115760). Other recommendations, such as expanding a cohort or lowering a dose will be made by a majority vote.

Regulatory and Ethical Considerations

This study will be conducted in accordance with the protocol and with:

- Consensus ethical principles derived from international guidelines including the Declaration of Helsinki and Council for International Organizations of Medical Sciences International Ethical Guidelines
- Applicable International Conference on Harmonisation (ICH) Good Clinical Practice (GCP) Guidelines
- Applicable ICH laws and regulations

The protocol, protocol amendments, informed consent form (ICF), Investigator's Brochure, and other relevant documents (eg, subject recruitment advertisements) must be submitted to an Institutional Review Board (IRB)/Independent Ethics Committee (IEC) by the investigator and reviewed and approved by the IRB/IEC. A copy of the written approval of the protocol and ICF must be received by Amgen before recruitment of subjects into the study and shipment of Amgen investigational product.

Amgen may amend the protocol at any time. The investigator must submit and, where necessary, obtain approval from the IRB/IEC for all subsequent protocol amendments and changes to the informed consent document. The investigator must send a copy of the approval letter from the IRB/IEC and amended protocol Investigator's Signature page to Amgen prior to implementation of the protocol amendment at their site.

The investigator will be responsible for the following:

- Providing written summaries of the status of the study to the IRB/IEC annually or more frequently in accordance with the requirements, policies, and procedures established by the IRB/IEC
- Obtaining annual IRB/IEC approval/renewal throughout the duration of the study. Copies of the investigator's reports and the IRB/IEC continuance of approval must be sent to Amgen
- Notifying the IRB/IEC of serious adverse events occurring at the site, deviations from the protocol or other adverse event reports received from Amgen, in accordance with local procedures
- Overall conduct of the study at the site and adherence to requirements of Title 21 of the U.S. Code of Federal Regulations (CFR), ICH guidelines, the IRB/IEC, and all other applicable local regulations

Informed Consent Process

An initial sample ICF is provided for the investigator to prepare the informed consent document to be used at his or her site. Updates to the sample ICF are to be communicated formally in writing from the Amgen Trial Manager to the investigator. The written ICF is to be prepared in the language(s) of the potential patient population.

The investigator or his/her delegated representative will explain to the subject, or his/her legally authorized representative, the aims, methods, anticipated benefits, and potential hazards of the study before any protocol-specific screening procedures or any investigational product(s) is/are administered and answer all questions regarding the study.

Subjects must be informed that their participation is voluntary. Subjects or their legally authorized representative defined as an individual or other body authorized under applicable law to consent, on behalf of a prospective subject, to the subject's participation in the clinical study will then be required to sign a statement of informed consent that meets the requirements of 21 CFR 50, local regulations, ICH guidelines, Health Insurance Portability and Accountability Act requirements, where applicable, and the IRB/IEC or study site.

The medical record must include a statement that written informed consent was obtained before the subject was enrolled in the study and the date the written consent was obtained. The authorized person obtaining the informed consent must also sign the ICF.

The investigator is also responsible for asking the subject if the subject has a primary care physician and if the subject agrees to have his/her primary care physician informed of the subject's participation in the clinical study unless it is a local requirement. The investigator shall then inform the primary care physician. If the subject agrees to such notification, the investigator is to inform the subject's primary care physician of the subject's participation in the clinical study. If the subject does not have a primary care physician and the investigator will be acting in that capacity, the investigator is to document such in the subject's medical record.

The acquisition of informed consent and the subject's agreement or refusal of his/her notification of the primary care physician is to be documented in the subject's medical records, and the ICF is to be signed and personally dated by the subject or a legally acceptable representative and by the person who conducted the informed consent discussion. Subject withdrawal of consent or discontinuation from study treatment

and/or procedures must also be documented in the subject's medical records; refer to Section 7.

Subjects must be re-consented to the most current version of the ICF (s) during their participation in the study.

The original signed ICF is to be retained in accordance with institutional policy, and a copy of the ICF(s) must be provided to the subject or the subject's legally authorized representative.

If a potential subject is illiterate or visually impaired and does not have a legally acceptable representative, the investigator must provide an impartial witness to read the ICF to the subject and must allow for questions. Thereafter, both the subject and the witness must sign the ICF to attest that informed consent was freely given and understood. (Refer to ICH GCP guideline, Section 4.8.9.)

A subject who is rescreened is not required to sign another ICF if the rescreening occurs within 30 days from the previous ICF signature date.

The ICF will contain a separate section that addresses the use of remaining mandatory samples for optional future research. The investigator or authorized designee will explain to each subject the objectives of the future research. Subjects will be told that they are free to refuse to participate and may withdraw their specimens at any time and for any reason during the storage period. A separate signature will be required to document a subject's agreement to allow any remaining specimens to be used for future research. Subjects who decline to participate will not provide this separate signature.

Data Protection/Subject Confidentiality

The investigator must ensure that the subject's confidentiality is maintained for documents submitted to Amgen.

Subject will be assigned a unique identifier by the sponsor. Any subject records or datasets that are transferred to the sponsor will contain the identifier only; subject names or any information which would make the subject identifiable will not be transferred.

On the Case Report Form (CRF) demographics page, in addition to the unique subject identification number, include the age at time of enrollment.

For serious adverse events reported to Amgen, subjects are to be identified by their unique subject identification number, initials (for faxed reports, in accordance with local laws and regulations), and age (in accordance with local laws and regulations).

Documents that are not submitted to Amgen (eg, signed ICFs) are to be kept in confidence by the investigator, except as described below.

In compliance with governmental regulations/ICH GCP Guidelines, it is required that the investigator and institution permit authorized representatives of the company, of the regulatory agency(s), and the IRB/IEC direct access to review the subject's original medical records for verification of study-related procedures and data. Direct access includes examining, analyzing, verifying, and reproducing any records and reports that are important to the evaluation of the study.

The investigator is obligated to inform and obtain the consent of the subject to permit such individuals to have access to his/her study-related records, including personal information.

Publication Policy

To coordinate dissemination of data from this study, Amgen may facilitate the formation of a publication committee consisting of several investigators and appropriate Amgen staff, the governance and responsibilities of which are set forth in a Publication Charter. The committee is expected to solicit input and assistance from other investigators and to collaborate with authors and Amgen staff, as appropriate, as defined in the Publication Charter. Membership on the committee (both for investigators and Amgen staff) does not guarantee authorship. The criteria described below are to be met for every publication.

Authorship of any publications resulting from this study will be determined on the basis of the Uniform Requirement for Manuscripts Submitted to Biomedical Journals International Committee of Medical Journal Editors Recommendations for the Conduct of Reporting, Editing, and Publications of Scholarly Work in Medical Journals, which states: Authorship credit is to be based on: (1) substantial contributions to conception and design, acquisition of data, or analysis and interpretation of data; (2) drafting the article or revising it critically for important intellectual content; (3) final approval of the version to be published; and (4) agreement to be accountable for all aspects of the work in ensuring that questions related to the accuracy or integrity of any part of the work are appropriately investigated and resolved. Authors need to meet conditions 1, 2, 3, and 4.

When a large, multicenter group has conducted the work, the group is to identify the individuals who accept direct responsibility for the manuscript. These individuals must fully meet the criteria for authorship defined above. Acquisition of funding, collection of

